#### *10.1.5.4.1 Final Visit - Visit 30 for study completers*

This visit will include:

- Record of concomitant medication
- Body weight measurement
- Physical examination including vital signs: SBP and DBP, heart rate
- Collect information on suspected efficacy endpoints
- Collection of cardiovascular events of interest other than efficacy endpoints (peripheral arterial disease, venous thromboembolic events)
- Collection of adverse events

- Data collection on IMP administration and IMP compliance check by review of diary and treatment kit accountability (used and unused kits)  
*NOTE: In case patient forgets to bring back diary at the visit, site should come up with an alternative solution to obtain as soon as possible information contained in patient diary in order to be able to complete final IMP information in eCRF.*
- Check of the compliance and stability of the dose of the LMT (atorvastatin, rosuvastatin, ± other LMT)
- 12-lead ECG
- Urinalysis (at selected sites), with urine sample sent to Central Lab
- Urine pregnancy test (females of childbearing potential only)
- Blood sample for:
  - Lipids: TC, LDL-C, HDL-C, TG, non-HDL-C, ApoB, ApoA-1, ratio ApoB/ApoA-1, and Lp (a)
  - Hematology: blood cell count including hematocrit, hemoglobin, red blood cell count, reticulocyte count, white blood cell count with differential count and platelets  
*NOTE: At selected sites with a longer transit time to Central Lab, a second hematology sample will be collected for local assessment of reticulocyte count*
  - Chemistry: glucose, sodium, potassium, chloride, bicarbonate, calcium, phosphorous, urea nitrogen, creatinine, uric acid, LDH, total protein, albumin, and  $\gamma$ GT
  - Liver panel (ALT, AST, ALP, and total bilirubin)
  - HbA1c
  - CPK
  - hs-CRP
  - Hepatitis C antibody test  
*NOTE: In case of positive hepatitis C antibody test at V30, patient should be recontacted as soon as possible after the site has been informed by Central Lab of this positive test, and a subsequent visit should be scheduled also as soon as possible, for collection of a confirmatory blood sample to be sent to Covance Central Lab.*
  - Library samples
  - Anti-alirocumab antibodies
- EQ-5D patient questionnaire
- IVRS/IWRS contact for notification of the date of this final visit; for patients still on treatment this will also be the end of treatment visit

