- And/or anti-diabetic medication initiated during the TEA E period with a confirmed diagnosis per the external diabetes experts *.

* Patients classified as NOD based only on the use of anti-diabetic medication during the TEAE period will be reviewed in a blinded manner by external experts in diabetology. If the diabetic mellitus status is not confirmed, the patients will not be classified as NOD.

- And/or at least 2 HbA_{1c} \geq 6.5% during the TEAE period
 - For patients with a single measurement available during the TEAE period, a single value $\geq 6.5\%$ will be considered and qualify the patient as NOD by default
 - For patients with several HbA1c measurements but only with the last one $\geq 6.5\%$, this single value $\geq 6.5\%$ will be considered and qualify the patient as NOD by default.
- And/or at least two fasting glucose measurements $\geq 126 \text{ mg/dL}$ (7.0 mmol/L):
 - For patients with only a single measurement available during the TEAE period, a single value ≥126 mg/dL (7.0 mmol/L) will NOT be considered and will NOT qualify the patient as NOD.
 - For patients with several fasting glucose measurements but only with the last one ≥126 mg/dL (7.0 mmol/L), this single value ≥ 126 mg/dL (7.0 mmol/L) will NOT be considered and will NOT qualify the patient as NOD.

Hepatitis C antibody

The number and percentage of patients with a post-baseline seroconversion for hepatitis C test will be provided by treatment group in post-baseline (including the TEAE and post TEAE periods). Post-baseline seroconversion is defined for patients with a negative baseline status who had either a "positive ribonucleic acid" (RNA) or a "confirmed positive antibody with negative RNA" post-baseline status as defined in the table below. Other situations require case by case evaluation and will be described individually if relevant.

The status as regards to hepatitis C virus (HCV) for a patient will be defined as follows for all evaluations (baseline and post-baseline).

	Hepatitis C Antibody (Ab) test result						
	Negative			Positive			
Reflexive test ^a – hepatitis C RNA test	Not available or HCV RNA not detected	HCV RNA detected	HCV RNA not detected ^b	HCV RNA detected	Not available		
Hepatitis C status - label	Negative	Positive RNA	Negative ^b	Positive RNA	Positive Ab – no RNA available		

Table 6 - Definition of the patient status regarding hepatitis C virus

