a Test performed at the same time or after the antibody test in the pre-treatment period (for baseline evaluation), or post-baseline, respectively

b For post-baseline evaluation, a second antibody test with a different type of assay is to be done at the same date or after the first antibody test. The result of this test will modify the final hepatitis C status of the patient in some cases (see details in the text below the table)

The baseline evaluation will be based on tests performed during the pre-treatment period.

In case of multiple hepatitis C tests available for the post-baseline evaluation, the positive status of the patient will be defined as follows:

- "Positive RNA" status if at least 1 post-baseline positive RNA is detected, regardless of status of the patient at the end of treatment.
- Else "Positive Ab no RNA available" status if no post-baseline reflexive RNA test is available for at least 1 post-baseline positive antibody test.

If no antibody test is available or with "indeterminate" as result pre-treatment or post-baseline, respectively, the RNA test (if available) will be used alone to determine the status of the patient. If no RNA is available then the hepatitis C status of the patient will be missing.

The post-baseline status "confirmed positive antibody with negative RNA" will replace "Negative" status as defined above in the case where no RNA was detected post-baseline and the 2 antibody tests surrounding the same visit (from 2 different types of assay) are positive.

For a conservative approach, the post-baseline status "Positive Ab - no RNA available" will not be modified by the availability of a second antibody test from a different assay.

Possible drug-induced liver injury

The liver function tests, namely AST, ALT, alkaline phosphatase, and total bilirubin, are used to assess possible drug-induced liver toxicity. The proportion of patients with PCSA values at any post-baseline visit by baseline status will be displayed by treatment group for each parameter.

A graph of distribution of peak values of ALT versus peak values of total bilirubin will also be presented. Note that the ALT and total bilirubin values are presented on a logarithmic scale. The graph will be divided into 4 quadrants with a vertical line corresponding to 3 x ULN for ALT and a horizontal line corresponding to 2 x ULN for total bilirubin.

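### The hepatitis C rule leaves out of the seroconversion count a patient positive on two antibody assays with no RNA result, although either RNA result would have counted

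*SAP*

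**What the plan says.** The hepatitis C part of SAP 3.4.5.3 promises the number and percentage of patients with post-baseline seroconversion by treatment group, as does Protocol 11.4.3.2. Seroconversion requires a negative baseline status and applies to patients "who had either a 'positive ribonucleic acid' (RNA) or a 'confirmed positive antibody with negative RNA' post-baseline status". Of everything else the SAP says: "Other situations require case by case evaluation and will be described individually if relevant".

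The final post-baseline status is assigned in order:

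- *Positive RNA* "status if at least 1 post-baseline positive RNA is detected, regardless of status of the patient at the end of treatment".
- Otherwise *Positive Ab - no RNA available* "status if no post-baseline reflexive RNA test is available for at least 1 post-baseline positive antibody test".
- *Confirmed positive antibody with negative RNA* replaces *Negative* where "no RNA was detected post-baseline and the 2 antibody tests surrounding the same visit (from 2 different types of assay) are positive".

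A closing sentence, beginning "For a conservative approach, the post-baseline status", fixes the second label: it "will not be modified by the availability of a second antibody test from a different assay".

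Two footnotes to Table 6 matter. Footnote a accepts as the reflexive test an RNA test done with the antibody test or after it. Footnote b plans a second, different antibody assay post-baseline, on the same date as the first or later.

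On collection, the flow chart in Protocol 1.2.1 schedules post-baseline hepatitis C antibody at V30 for study completers and at V70. If the V30 test is positive, Protocol 10.1.5.4.1 requires the patient to be recontacted: "a subsequent visit should be scheduled also as soon as possible, for collection of a confirmatory blood sample".

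**The concern.** A rule for missing data should matter only where the missing value could have changed the classification. For a patient positive on two assays, both possible RNA results lead to seroconversion, so the missing result carries no information for this table. The rule nevertheless takes the patient out of the numerator.

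The SAP foresees this patient: the closing sentence has a purpose only if a second assay can be available when RNA is not. A missing RNA result is also plausible at V30, because the confirmatory blood needs one more visit after what was meant to be the last one.

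What is at stake is the by-arm number and percentage of seroconversions. Where such patients exist, both figures are understated.

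**Working it through.** The plan gives no figure to reproduce, because this is a classification rule. The check is to apply Table 6, its footnotes and the text below it to every combination of results for a baseline-negative patient at one post-baseline visit.

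Inputs:

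- first assay: negative or positive
- second assay: negative, positive or not available
- RNA: detected, not detected or not available

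That gives 2 × 3 × 3 = 18 combinations.

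With a positive first assay:

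| Second assay | RNA | Final status | Counted? |
|---|---|---|---|
| positive | detected | Positive RNA | yes |
| positive | not detected | confirmed positive antibody with negative RNA | yes |
| positive | missing | Positive Ab - no RNA available | **no** |
| negative | detected | Positive RNA | yes |
| negative | not detected | Negative | no |
| negative | missing | Positive Ab - no RNA available | no |
| missing | detected | Positive RNA | yes |
| missing | not detected | Negative | no |
| missing | missing | Positive Ab - no RNA available | no |

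With a negative first assay, the three combinations with RNA detected are counted and the other six are *Negative*.

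Total counted: 6 combinations with RNA detected, plus 1 with both assays positive and RNA not detected, which is 7 of 18.

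Now compare the rows with RNA missing. When the second assay is negative or absent, the two possible RNA results lead to different answers (yes and no), so leaving the patient unclassified is reasonable. When the second assay is positive, both lead to yes. That is the only combination in which the missing result is irrelevant and the patient is still left out. Counting it gives 7 + 1 = 8 of 18, and no other combination changes.

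**Several post-baseline tests.** Order matters here.

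1. *Antibody positive without RNA first, confirmed positive with negative RNA later.* Under footnote a the later RNA test can serve as the reflexive test for the earlier antibody. The condition for the RNA-unavailable label is then not met, and the confirmed status can apply.
2. *Confirmed first, then a later antibody-positive sample with no RNA at or after it.* The condition for the RNA-unavailable label is met. The confirmed status may replace only *Negative*, so on a literal reading the confirmed seroconversion leaves the count.

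The second order needs two post-baseline antibody tests. It should be rare, because the reduced V30 for prematurely discontinued patients (Protocol 10.1.5.4.2) has no hepatitis C test. It is not excluded: footnote m of the flow chart limits the reduced visit to cases where V30 falls more than 6 months after V70.

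**The case against.** The best defence is that the closing sentence is conservative in an important case: a negative second assay cannot clear an antibody-positive patient whose RNA is unknown. That stands, and the fix keeps it. But the same sentence also blocks the upgrade when the second assay is positive, and there it works against caution.

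A second defence is that these patients keep a positive label and go to case-by-case review. For a rare event, that is a sensible supplement. But individual description is promised only where relevant, and nothing returns the patient to the number and percentage.

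A third is that the affected group may be empty. Footnote b is attached to the result with RNA not detected, and the documents do not say whether the second assay uses the original sample or the confirmatory one. If it uses the confirmatory one, a patient who never returns has neither result and is not double-positive. This stands as a limit on size, not on the logic.

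Three stronger readings are tempting and are not supported:

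- A reader might infer that the count falls in proportion to the patients who do not return after V30. A non-returner may lack the second assay too, so no percentage loss follows.
- A reader might treat V70 like V30. Patients remain in the study after V70 with scheduled visits (Protocol 10.1.5.3 and 10.3.4), the confirmatory sample can be taken at one of them, and footnote a accepts a later RNA result.
- A reader might infer that an early antibody-positive test without RNA cancels a later confirmed result. Footnote a gives the answer to that; only the reverse order is a problem.

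**Conclusion.** The point holds for one defined patient: negative at baseline, positive on two different antibody assays surrounding the same post-baseline visit, with no RNA result. By the SAP's own definition either RNA result would make this patient a seroconverter, yet the patient is not counted. The order of precedence also leaves a smaller gap when a confirmed result is followed by an antibody-positive sample without RNA.

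The conclusion rests on the text alone. Its size cannot be computed: the documents give no rate of antibody positivity, of missing RNA or of available second assays, and no ground to expect a difference between arms. The number is likely to be very small and may be zero. The table is descriptive (Protocol 11.4.3 plans no formal testing of safety data), and efficacy is untouched. This is a minor correction worth making because it is cheap.

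**What to change.** In the hepatitis C part of SAP 3.4.5.3:

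1. Count as seroconversion any baseline-negative patient with positive antibody tests from two different assays surrounding the same post-baseline visit, whether RNA is detected, not detected or missing.
2. Keep *Positive Ab - no RNA available* for patients without a positive second assay. A negative or missing second assay leaves that label unchanged, which preserves the protection the authors wanted.
3. State that a confirmed positive status is not displaced by a later antibody-positive sample without RNA.

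If the sponsor prefers not to alter the definition, the least change is a separate row by treatment group for double-positive patients with RNA missing.

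The cost is a couple of sentences and a small edit to the derivation, best made before treatment codes are opened. The only drawback is that the reported count may become slightly less favourable: it can rise or stay the same, but not fall.

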3.4.5.4 Analyses of vital sign variables

The summary statistics (including number, mean, median, Q1, Q3, standard deviation, minimum, and maximum) of all vital signs variables (values and changes from baseline) will be calculated for each visit or study assessment (baseline, each post-baseline time point, last on-treatment and worst on-treatment value) by treatment group during the treatment period. In addition, for some parameters of interest, mean changes from baseline with the corresponding standard error could be plotted over time in each treatment group.

The incidence of PCSAs at any time during the TEAE period will be summarized by treatment group irrespective of the baseline level and/or according to the following baseline status categories:

- Normal/missing;
- Abnormal according to PCSA criterion or criteria.

3.4.6 Analyses of other safety parameters

Events initially suspected by investigators, and reported as such in endpoints forms, may finally not be confirmed by investigators and possibly classified into another category that is not a component of the primary efficacy endpoint. In addition, per protocol all suspected UAs have to be sent for adjudication regardless of whether the event fulfils the stricter protocol definition or not, therefore a high proportion of the reported UAs are expected to be finally not retained as an endpoint.

Since those events are not reported as adverse events either, they will be described separately as follows:

The number (%) of patients with events below during the TEAE period will be displayed by treatment group on the safety population:

- With final diagnosis as per investigator of stable coronary disease,
- With final diagnosis as per investigator of unstable angina regardless of whether the event fulfils the stricter protocol definition or not;
- With final diagnoses as per investigator of hemorrhagic stroke, transient ischemic attack (TIA), and subdural hematoma.

The number (%) of patients with hemorrhagic strokes or silent MI as per CEC during the TEAE period will also be summarized on the safety population

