#### **9.1.7.3 Congestive Heart Failure requiring hospitalization.**

Congestive Heart Failure (CHF) requiring hospitalization is defined as an event that meets ALL of the following criteria:

- 1) The patient is admitted to the hospital or emergency room (until at least next calendar day) with a primary diagnosis of CHF
- 2) The patient exhibits documented new or worsening symptoms due to CHF on presentation, including at least ONE of the following:
  - a) Dyspnea (dyspnea with exertion, dyspnea at rest, orthopnea, paroxysmal nocturnal dyspnea)
  - b) Decreased exercise tolerance
  - c) Fatigue
  - d) Other symptoms of worsened end-organ perfusion or volume overload
- 3) The patient has objective evidence of new or worsening CHF, consisting of at least TWO physical examination findings OR one physical examination finding and at least ONE laboratory/imaging/hemodynamic criterion), including:
  - a) Physical examination findings considered to be due to heart failure, including new or worsened:
    - Peripheral edema.
    - Increasing abdominal distension or ascites (in the absence of primary hepatic disease)

- Pulmonary rales/crackles/crepitations
  - Increased jugular venous pressure and/or hepatjugular reflux
  - S3 gallop
  - Clinically significant or rapid weight gain thought to be related to fluid retention
- b) Laboratory, imaging or hemodynamic evidence of new or worsening CHF, including:
- Increased B-type natriuretic peptide (BNP)/ N-terminal pro-BNP (NT-proBNP) concentrations consistent with decompensation of heart failure. In patients with chronically elevated natriuretic peptides, a significant increase should be noted above baseline
  - Radiological evidence of pulmonary congestion
  - Hemodynamic evidence from right-heart catheterization (e.g. elevated pulmonary capillary wedge pressure, elevated central venous pressure, or low cardiac index) or from left heart catheterization (elevated left ventricular end-diastolic pressure)
- 4) The patient receives initiation or intensification of treatment specifically for HF, including at least ONE of the following:
- a) Significant augmentation in oral diuretic therapy
  - b) Intravenous diuretic, inotrope, or vasodilator therapy
  - c) Mechanical or surgical intervention, including:
    - Mechanical circulatory support (eg, intra-aortic balloon pump, ventricular assist device)
    - Mechanical fluid removal (eg, ultrafiltration, hemofiltration, dialysis)

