### **9.2.1 Adverse event**

All adverse events diagnosed by the Investigator, irrespective of the result of the adjudication for cardiovascular events, will be reported and described.

All AEs will be coded to a “Lowest Level Term (LLT)”, “Preferred Term (PT)”, “High Level term (HLT)”, “High Level Group Term (HLGT)” and associated primary “System Organ Class (SOC)” using the version of MedDRA (Medical Dictionary for Regulatory Activities) currently in effect at Sanofi at the time of the considered database lock.

AEs of special interest include, but are not limited to, the following:

- Allergic events (using special eCRF pages, see [Section 10.6.2](#))
- Local injection site reactions (using special eCRF pages, see [Section 10.6.1](#))
- Hemolytic anemia (using special eCRF pages, see [Section 10.4.7.1](#))

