#### **10.4.3 Serious adverse events waived from expedited regulatory reporting to health authorities**

Unlike most studies where the primary efficacy variable is the resolution or improvement of an existing condition, in this study efficacy outcomes include the occurrence of life-threatening events. Indeed, participants to this study are recruited precisely because they are at high risk for these life threatening events. They are therefore expected to have at least one cardiovascular efficacy endpoint during the course of the study.

In light of the above, (primary and secondary) suspected cardiovascular efficacy endpoints as specified in this protocol will not be considered as AEs and are waived from regulatory reporting to Health Authorities except if the Investigator according to his/her best medical judgment considers these events as unexpected in the context of the underlying disease condition. In that case, the Investigator will complete an AE/SAE form (in addition to eCRF efficacy endpoint page – see below) including causality assessment within 24 hours.

For this study, all suspected cardiovascular efficacy endpoints will be reported (within 24 hours) in the specific eCRF efficacy endpoint pages; the system will automatically send the notification to the Clinical Event Committee Coordination Center at DCRI. This automatic notification will occur after the Investigator has approved the eCRF screens or after a standard time interval has elapsed, whichever comes first.

Expedited reporting to Health Authorities for the following cardiovascular outcomes will be waived:

- CV death including CHD death
- All other causes of death
- Non-fatal MI
- Non-fatal stroke
- Unstable angina requiring hospitalization
- Ischemia-driven coronary revascularization procedure
- Congestive heart failure requiring hospitalization

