3.1.3.2 Secondary efficacy endpoint(s)

Clinical events assessed in the analyses are those determined by the CEC. Events suspected by the investigator but not confirmed by the CEC will not be part of the outcomes. CHD death outcome will include deaths for causes that could not be determined by the CEC (adjudicated as "Undetermined cause of death"). Similarly, fatal and non-fatal ischemic stroke outcomes will include fatal and non-fatal strokes for causes that couldn't be determined by the CEC (adjudicated as "Stroke not otherwise specified").

Rules for censoring date and for imputation of incomplete dates of events will be the same as for the primary efficacy endpoint, for all secondary efficacy endpoints with the exception of the analyses of the time to CHD death, the time to CV death and of the time to all-cause mortality for which the censoring date will be defined as the earliest date among the "date of last known alive or Date of death" and the cut-off date/CSED.

The "date of last known alive or Date of death" will be the latest date among:

- The date of last visit performed;
- The "Date of last known alive or Date of death" reported in the visit e-CRF pages during the course of the study;
- The "Date of last known alive or Date of death" reported at the end of the study for all patients (this information can also be completed during the course of the study for "lost-to-follow-up" patients, patients who discontinued the follow-up and patients who died);

• The latest date among these dates, the last IMP injection date, the date of adverse events, the date of CV events, the date of death and the date of laboratory samples will be considered.

In case at time of database extraction for the interim analyses, only the randomization date is available, then the censoring date will be the randomization date.

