- Second interim analysis date (futility and overwhelming efficacy): when 1210 patients have experienced at least 1 primary efficacy event (75% fraction information);
- Final analysis date: when 1613 patients have experienced at least 1 primary efficacy event or 24 months after the last date of randomization ex-China, whichever comes last.

Sensitivity analyses

The following sensitivity analyses will be performed:

Primary efficacy endpoint as per investigator

A sensitivity analysis of the primary efficacy endpoint will be performed including any events up to the CSED with final diagnosis by the investigator confirming the event, whether or not confirmed by the CEC. The statistical methodology used will be the same as defined for the primary efficacy analysis.

Since Investigators are requested to report any UA regardless of whether the event fulfils the stricter protocol definition or not, a subset of the reported UA will be selected using information reported on the e-CRF on hospitalization forms, additional information reported on the UA form related to ECG findings, need for revascularization procedure, and/or the concomitance of elevation of cardiac biomarkers (see Appendix C for full details). Since the categorization of deaths as CHD death was not requested from the Investigator, CHD deaths as per Investigator will include all deaths with primary cause of death reported as "Acute myocardial infarction", "Sudden cardiac death", "Heart failure or cardiogenic shock" as per investigator. The category "Undetermined cause of death" as per Investigator will be also included in this endpoint.

The concordance rate between Investigator opinion and adjudication by the CEC will be provided for all CV events adjudicated, by CV event's type.

Primary endpoint analysis excluding undetermined causes of death and undetermined causes of stroke

The primary efficacy analysis will be also performed excluding deaths adjudicated as "undetermined causes of death" and strokes adjudicated as "undetermined causes of stroke" by the CEC.

Supportive analyses

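### Heart-failure hospitalizations and coronary revascularizations that the investigator reports but the CEC rejects have no planned table by treatment group

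*SAP*

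**What the plan says.** **Adverse event status.** Protocol 10.4.3 applies to the primary and the secondary endpoints alike, and its rule reads: "suspected cardiovascular efficacy endpoints as specified in this protocol will not be considered as AEs and are waived from regulatory reporting to Health Authorities". The exception is an event that the investigator "considers these events as unexpected in the context of the underlying disease condition"; that event also gets an AE/SAE form. The list of waived outcomes in the same section names seven types, among them congestive heart failure requiring hospitalization and ischemia-driven coronary revascularization.

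**Outcome status.** Protocol 9.1 and SAP 3.1.3.2 agree. In the SAP's words: "Events suspected by the investigator but not confirmed by the CEC will not be part of the outcomes". For heart failure the bar is a conjunction: under Protocol 9.1.7.3 the endpoint "is defined as an event that meets ALL of the following criteria", and there are four of them.

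**What is recovered.** SAP 3.4.6 gives its reason, "Since those events are not reported as adverse events either, they will be described separately as follows", and then tabulates by treatment group, on the safety population in the TEAE period, five diagnoses as per investigator and two as per CEC. SAP 3.4.4.1 adds an investigator-based analysis: "A sensitivity analysis of the primary efficacy endpoint will be performed including any events up to the CSED". It also plans an investigator-CEC concordance rate for all adjudicated cardiovascular events by event type, with no mention of treatment group.

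**General safety statement.** Protocol 9.2.1 says that adverse events diagnosed by the investigator, "irrespective of the result of the adjudication for cardiovascular events, will be reported and described".

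**The concern.** An event can be kept off the adverse event tables because it was a suspected endpoint, and then kept off the efficacy tables because the CEC did not accept it. SAP 3.4.6 exists to close that hole, but its list is closed and omits two of the event types to which Protocol 10.4.3 applies.

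An admission for heart failure can fail Protocol 9.1.7.3 for want of one documented finding and still be a clinical event of interest. Where it is an inpatient admission, it meets the protocol's seriousness criterion in 10.4.1.2. If such events are shown nowhere by arm, the efficacy and adverse event sections of the report can each look complete while a class of cardiac events sits in neither. A reader could not then check whether the rejected events were balanced between the groups.

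**Working it through.** No rate, sample size or alpha is at issue, so the check is one of coverage. Each of the seven event types waived in Protocol 10.4.3 was followed, after CEC rejection, through every planned analysis that shows results by treatment group.

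| Waived type (Protocol 10.4.3) | Where it is still visible by arm if the CEC rejects it | Covered? |
|---|---|---|
| CV death, including CHD death | All-cause mortality (SAP 3.1.3.2.1); death summaries (SAP 3.4.5.2) | Yes |
| Death from other causes | Same | Yes |
| Non-fatal MI | Investigator-defined primary composite (SAP 3.4.4.1) | Yes, inside a composite |
| Non-fatal stroke | Ischemic: investigator-defined composite. Hemorrhagic: SAP 3.4.6 | Yes |
| Unstable angina | SAP 3.4.6; a subset also in the investigator-defined composite | Yes |
| Ischemia-driven revascularization | None found | No |
| Heart failure hospitalization | None found | No |

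Result: 5 of 7 covered, 2 of 7 not.

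Other routes that might have rescued the last two rows:

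1. **Investigator-based sensitivity analysis.** It is confined to the primary composite (SAP 3.1.3.1). Heart failure hospitalization and revascularization are other secondary endpoints (SAP 3.1.3.2.2); revascularization also enters some main secondary composites, but only as confirmed by the CEC.
2. **Concordance rate.** It spans all adjudicated event types, so it should show how far the CEC disagreed with investigators on heart failure. As written it does not say in which arm.
3. **Cardiovascular events of interest (SAP 3.1.5.7).** Peripheral arterial disease and venous thromboembolism only.
4. **Separate description of unconfirmed events (Protocol 9.1.1).** Promised for the primary outcome only.
5. **Adverse event tables.** They take in only those events that the investigator judged unexpected and that fall in the TEAE period.
6. **Protocol 9.2.1.** It speaks of adverse events. Protocol 10.4.3 has already taken suspected endpoints out of that term, so 9.2.1 does not bring them back.

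A rejected revascularization may accompany an entry for MI, unstable angina or stable coronary disease, but the procedure itself is not counted.

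A third group is less certain. If an investigator first suspects an endpoint and settles on a diagnosis outside the SAP 3.4.6 list, the text does not say whether the event moves to the adverse event page or stays on the endpoint page. If it stays, it too is untabulated.

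**The case against.** The best answer is that most of the clinical signal is already shown. CEC-confirmed heart failure hospitalization is a time-to-event endpoint compared by arm in the ITT population (SAP 3.1.3.2.2 and 3.4.4.2). The CEC is blinded, so nothing suggests that rejection differs by arm. Heart-failure deaths reach the death summaries, and those so attributed by the investigator enter the investigator-defined composite. During the trial the DMC sees unblinded cardiovascular outcomes whether adjudicated or not (Protocol 6.4). All of this stands, and it is why the gap is modest.

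It is also fair to say that the opening of SAP 3.4.6 describes a neighbouring class: events that the investigator went on to reclassify, and unstable anginas outside the strict definition. It does not itself say how an investigator-confirmed, CEC-rejected heart failure event is handled. That follows from Protocol 10.4.3 together with SAP 3.1.3.2.

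Several stronger readings are tempting and not supported:

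- **That rejected heart failure events appear in no table at all.** Events judged unexpected get an AE/SAE form, and the concordance table should include them without a stated split by arm.
- **That the plan hides any imbalance in heart failure.** Confirmed events are compared by arm.
- **That every rejected event is a serious hospitalization.** One ground for rejection is failing the first criterion of Protocol 9.1.7.3, which requires a stay to at least the next calendar day with heart failure as the primary diagnosis.
- **That Protocol 9.2.1 is breached.** The two sections use the term adverse event differently. That is a tension to reconcile, not a broken commitment.
- **That a count of lost events can be given.** The documents contain neither a rate of suspected heart failure admissions nor a CEC rejection share, and the SAP 3.4.6 tables are limited to the TEAE period, so full follow-up is the wrong base.

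**Conclusion.** The gap is real and narrow. Following the plan as written, heart failure hospitalizations and ischemia-driven revascularizations that the investigator reports and the CEC rejects have no efficacy or safety table by treatment group, unless the investigator judged the event unexpected. That is two of the seven waived event types. How many patients this touches cannot be derived from the documents.

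The conclusion rests on the main text of both documents. Protocol Appendix E (reporting instructions for adverse events and suspected endpoints) and SAP Appendix C (endpoint derivation) could not be checked. A rule there could close part of the gap and should be looked for first. The primary result and type I error control are unaffected; what is at stake is completeness of the by-arm cardiac safety description.

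**What to change.** 1. In SAP 3.4.6 add, by treatment group on the safety population during the TEAE period, the number (%) of patients with investigator-reported heart failure hospitalization and the number (%) with coronary revascularization, each whether or not confirmed by the CEC.
2. Add one line for any other investigator final diagnosis that remains on the endpoint pages and was not reported as an adverse event.
3. Present the investigator-CEC concordance table in SAP 3.4.4.1 by treatment group.
4. Reconcile Protocol 9.2.1 with 10.4.3, so that it is clear whether unconfirmed suspected endpoints belong among the events to be described.

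A pooled summary of serious events is not needed for this purpose. Adding only rejected events to those on the adverse event pages would still leave out confirmed endpoints and could count twice an event carrying both forms. If such a summary is produced, it should include confirmed endpoints and count each patient once.

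The cost is SAP wording and one or two extra descriptive tables, with no alpha spent. The concordance analysis already requires the investigator's opinion for every adjudicated event type, so new data collection should not be needed, although the documents do not describe the final-diagnosis field for heart failure specifically.
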